A phase 1, single-center, double-blind, placebo-controlled clinical study to evaluate the safety, tolerability, and pharmacokinetics of TNP-2092 Capsules, and the food effect on the pharmacokinetics of TNP-2092 Capsules after single-dose oral administration in healthy subjects.

Protocol

Protocol No.: TNP-2092-01

Approval Date: 19 May 2016

ClinicalTrials.gov ID: NCT06178718

Protocol Synopsis of Study TNP-2092-01

Name of Sponsor Company: TenNor Therapeutics (Suzhou) Limited.	Individual Study Table Referring to Part of the Dossier	(For National Authority Use Only)
Name of Finished Product: TNP-2092 capsules	Volume: Page:	
Name of Active Ingredient: TNP-2092		
Title of study: A phase 1, single-center, double-blind, placebo-controlled clinical study to evaluate the safety, tolerability, and pharmacokinetics of TNP-2092 Capsules, and the food effect on the pharmacokinetics of TNP-2092 Capsules after single-dose oral administration in healthy subjects		
Investigator: [name], The First Hospital of Jilin University		
Study center: A single center.		
Clinical Phase: 1		
Objectives 1) To evaluate the safety and tolerability of TNP-2092 Capsules in healthy subjects after single-dose escalated oral administration. 2) To evaluate the pharmacokinetic characteristics of TNP-2092 Capsules. 3) To evaluate the effect of eating on the pharmacokinetics of TNP-2092 Capsules after single-dose oral administration in healthy subjects.		

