Methodology This is a single-center, randomized, double-blind, placebo-controlled, dose-ascending single-dose-administration study, and a study on the food effects on pharmacokinetics. Five dose groups of 100 mg, 200 mg, 400 mg, 800 mg, and 1200 mg will be set up. The 100 mg, 200 mg, 800 mg, and 1200 mg groups will complete the single administration clinical study, with 10 subjects randomized in each group, 8 subjects receiving TNP-2092 and 2 receiving placebo. The drug will be administered once in each group in the fasting state, and tolerability will be evaluated on D4. Subjects were sequentially enrolled into different dose groups in ascending order of dose, and only when the previous lower dose was confirmed to be safe and well tolerated could they be enrolled into the next higher dose group. The 400 mg group will complete the clinical study on single administration and the effects of eating on pharmacokinetics and undergo the metabolic transformation evaluation. A total of 18 subjects will be enrolled in the group and randomized into Group A and Group B, with 8 subjects receiving the investigational product and 1 receiving placebo. The drugs will be administered in the fasting state and in the fed state for two cycles, with a wash-out period of 4 days. In terms of the administration sequence, Group A will first take TNP-2092 Capsules or placebo in the fasting state, and then TNP-2092 Capsules or placebo in the fed state; Group B will first take TNP-2092 Capsules or placebo in the fed state, and then TNP-2092 Capsules or placebo in the fasting state. Tolerability evaluation will be conducted on D4 and at the end of the study of food effects on pharmacokinetics (D8). The study of the 400 mg group is conducted on the premise that the tolerability evaluation result of the 200 mg group is favorable. After that, if the tolerability evaluation result in the 400 mg group is favorable for the first cycle, the second-cycle clinical study of the 400 mg group and the 800 mg group could be conducted in parallel.		

Name of Sponsor Company: TenNor Therapeutics (Suzhou) Limited.	Individual Study Table Referring to Part of the Dossier Volume: Page:	(For National Authority Use Only)
Name of Finished Product: TNP-2092 capsules		
Name of Active Ingredient: TNP-2092		

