During the study, blood samples will be collected from the subjects at the specified time points and used for pharmacokinetic analysis. Also, urine and stool samples will be collected from Group A in the 400 mg group in the first cycle for the metabolic transformation study.

- Plasma sample
 - 100 mg, 200 mg, 800 mg and 1200 mg dose groups: For each group, samples are collected before the first (D1) administration (within 15 minutes), and 0.5 h, 1 h, 2 h, 3 h, 4 h, 6 h, 8 h, 10 h, 12 h, 16 h, 24 h, 36 h, 48 h and 72 h after administration, with 4 mL collected at each time point.
 - 400 mg dose group
 - ◆ Day 1: Before administration (within 15 minutes), and 0.5 h, 1 h, 2 h, 3 h, 4 h, 6 h, 8 h, 10 h, 12 h, 16 h, 24 h, 36 h, 48 h and 72 h after administration.
 - ◆ Day 5: Before administration (within 15 minutes), and 0.5 h, 1 h, 2 h, 3 h, 4 h, 6 h, 8 h, 10 h, 12 h, 16 h, 24 h, 36 h, 48 h and 72 h after administration.
- Urine sample
 - Group A of the 400 mg dose group: Urine samples are collected at 0 h before administration on D1, and 0-6 h, 6-12 h, 12-24 h, 24-48 h and 48-72 h after administration.
- Stool sample
 - Group A of the 400 mg dose group: Stools are collected whenever available within 72 hours after administration on D1.

Number of subjects

It is planned to enroll 58 subjects. Ten subjects will be administrated with placebo, and 48 subjects will be administrated with TNP-2092 capsules (8 subjects each with 100 mg, 200 mg, 800 mg or 1200 mg and 16 subjects with 400 mg).

Diagnosis and main criteria for inclusion

Each subject is required to meet all of the following criteria to be eligible for study enrollment:

- 1) Adult males or females
- 2) Eighteen to 45 years of age, inclusive
- 3) BMI: 19.0-26.0 kg/m², including 19.0 and 26.0 kg/m²
- 4) Female subjects of childbearing potential must agree to abstinence or take effective contraceptive measures during the trial and at least 70 days (10 weeks) after administration
- 5) Male subjects must agree to abstinence or use condoms as a contraceptive measure during the trial and at least 70 days (10 weeks) after administration
- 6) Subjects whose clinical laboratory test results are within the normal range or abnormal tests are judged to be no clinical insignificance by the investigator

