Investigational product, dose and regimen of administration 
Investigational product: TNP-2092 capsules
 
Dose and regimen of administration: the doses were 100 mg, 200 mg, 400 mg, 800 mg, and 1,200 mg. For the administration in the fasted state, subjects are required to fast overnight for at least 10 hours and to take capsule with 240 ml of warm water. For the administration in the fed state, subjects are required to fast overnight for at least 10 hours and take high-fat meal 30 min before receiving capsule with 240 mL warm water. Meals should be controlled to finish just before administration.
		
Duration of treatment Approximately up to 22 days from signing ICF to the end of the study).		
Reference treatment, dose and regimen of administration 
Placebo: TNP-2092 placebo capsules
 
Dose and regimen of administration: the same regimen as that of TNP-2092 capsules.
		
Criteria for evaluation Pharmacokinetics		

Name of Sponsor Company: TenNor Therapeutics (Suzhou) Limited.	Individual Study Table Referring to Part of the Dossier Volume: Page:	(For National Authority Use Only)
Name of Finished Product: TNP-2092 capsules		
Name of Active Ingredient: TNP-2092		

T_{max}, C_{max}, $t_{1/2}$, $AUC_{0-\infty}$, AUC_{0-t}, the amount of drug excreted in the urine at 72 hours after administration (Ae_{0-t}), the amount of drug excreted in feces at 72 hours after administration (Ae_{0-t}), the cumulative drug excretion rate in urine, the cumulative drug excretion rate in feces, and CL.
		

Safety incidence of AEs, the relationship between the drug and AEs, severity of AEs, physical examination, clinical laboratory tests (hematology, blood chemistry, coagulation and urine test), vital signs (blood pressure, pulse and body temperature) and 12-lead ECG.
		

Efficacy Not applicable.
		

Statistical methods SAS 9.4 will be used for the statistical analysis.
		

Sample size simulation This study is a early phase exploratory clinical trial, and the sample size was not based on statistical hypothesis test. Study sample size is chosen based on the assessment of safety, PK, and preliminary efficacy in line with similar trials. The sample size of 10 subjects per group, and additional 8 subjects in the 400 mg group for food effect study are also appropriate for the purpose of the exploration of the PK profile and safety of TNP-2092 capsules.
		

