
Population for analyses
 
 • Full Analysis Set (FAS): all the subjects who were randomized into groups. • Safety Analysis Set (SS): all the subjects who have been randomized into groups and received at least one dose of study drug. • PK Concentration Analysis Set (PKCS): all the subjects who have been randomized into groups, received at least one dose of study drug, and have at least one evaluable blood drug concentration. • PK Parameter Analysis Set (PKPS): all subjects who have been randomized into groups, have received at least one dose of study drug, and have at least one evaluable pharmacokinetic parameter. • Bioequivalence Set (BES) of food effect: All subjects with no significant protocol violations, no protocol deviations that had impact on PK endpoints (e.g., AUC, C_{max}), who must have received at least one cycle of treatment in the crossover study and have at least one evaluable pharmacokinetic parameter. 		

Interim analysis No interim analysis is planned.
		

PK analysis PK parameters will be estimated by non-compartmental method using WinNonlin 6.4. Pharmacokinetic analysis will be based on the PKPS. Pharmacokinetic concentration and parameters will be subjected to descriptive analysis by dose group. The mean and individual drug-time curves will be shown graphically. Numbers will include individual values and mean values. In addition, individual and mean dose standardization parameters will be plotted against the dose to evaluate whether there are any obvious trends.
		

Name of Sponsor Company: TenNor Therapeutics (Suzhou) Limited.	Individual Study Table Referring to Part of the Dossier Volume: Page:	(For National Authority Use Only)
Name of Finished Product: TNP-2092 capsules		
Name of Active Ingredient: TNP-2092		
Food effect analysis		

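### Minor improvement: the dose trend is to be judged from descriptive statistics and a plot only; an exploratory power-model slope with a 90% CI on fasted profiles would show how precisely it is known

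*Combined protocol and SAP*

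**What the plan says.** The second objective in the synopsis reads "To evaluate the pharmacokinetic characteristics of TNP-2092 Capsules". Dose proportionality is not named as an objective.

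Under Statistical methods, PK analysis, the plan is that "Pharmacokinetic concentration and parameters will be subjected to descriptive analysis by dose group" and that "individual and mean dose standardization parameters will be plotted against the dose to evaluate whether there are any obvious trends". The synopsis and the two procedure schedules contain no model, slope or interval for the dose relation. The one modelled PK comparison is the food effect, an analysis of variance on log-transformed AUC and Cmax that reports geometric mean ratios with 90% CIs.

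The doses are 100, 200, 400, 800 and 1200 mg. Active subjects are "8 subjects each with 100 mg, 200 mg, 800 mg or 1200 mg and 16 subjects with 400 mg". In the four groups other than 400 mg, "The drug will be administered once in each group in the fasting state". In the 400 mg group, "The drugs will be administered in the fasting state and in the fed state for two cycles, with a wash-out period of 4 days"; within it, "Group B will first take TNP-2092 Capsules or placebo in the fed state, and then TNP-2092 Capsules or placebo in the fasting state". On size, the synopsis says that "the sample size was not based on statistical hypothesis test".

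**The concern.** The plan asks whether dose-standardised parameters change with dose and leaves the answer to the eye. With 8 active subjects at most doses, a flat-looking plot is ambiguous: exposure may be close to proportional, or the scatter may hide a real departure. Descriptive statistics show the spread at each dose. They do not say how large a trend across the 12-fold range is still compatible with the data.

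What is at stake is how much a reader can take from the PK results on this one question. Safety, escalation and the food-effect analysis are not affected.

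**Working it through.** **Inputs from the synopsis.** Five doses, 100 to 1200 mg (1200/100 = 12-fold). Active subjects 8/8/16/8/8. The counts agree with the stated enrolment: active 4×8 + 16 = 48, placebo 4×2 + 2×1 = 10, total 58. The plan states no power or precision figure for the dose trend, so there is none to reproduce.

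**Assumptions.** Between-subject CV of 30, 40, 50 or 80% (none is given), constant across doses; all active subjects evaluable; one fasted profile per subject.

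**Model.** ln(parameter) = a + b × ln(dose). Proportionality is b = 1. The dose-normalised ratio of 1200 to 100 mg is 12^(b−1).

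**Spread of ln(dose).** The mean over the 48 subjects is 5.944. Squared distances from it are 1.791, 0.416, 0.002, 0.549 and 1.315 from the lowest to the highest dose. Sxx = 8 × (1.791 + 0.416 + 0.549 + 1.315) + 16 × 0.002 = 32.6 (unrounded 32.61).

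**Half-width of the 90% CI for b** = t(0.95, 46) × σ / √Sxx, with t = 1.679 and σ = √ln(1 + CV²). At CV 50%: σ = √ln(1.25) = 0.472, and 1.679 × 0.472 / √32.61 = 0.139.

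| Assumed CV | σ | Half-width for b | Factor on 1200 vs 100 mg ratio (12^half-width) |
|---|---|---|---|
| 30% | 0.294 | 0.086 | 1.24 |
| 40% | 0.385 | 0.113 | 1.33 |
| 50% | 0.472 | 0.139 | 1.41 |
| 80% | 0.703 | 0.207 | 1.67 |

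So if the estimated slope were exactly 1 at CV 50%, the interval would still allow a dose-normalised ratio from 0.71 to 1.41. A plot alone does not convey that.

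**What the interval can detect** (noncentral t, 46 degrees of freedom). Probability that the 90% CI excludes 1 at CV 30/40/50/80%:

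- True b = 0.80 (ratio 12^−0.2 = 0.61): 0.99/0.90/0.77/0.48.
- True b = 0.90 (ratio 12^−0.1 = 0.78): 0.61/0.43/0.33/0.21.

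**Group A, cycle 1 only at 400 mg** (8/8/8/8/8). Sxx = 32.58 with 38 degrees of freedom; half-widths are 0.087/0.114/0.140/0.208. Almost nothing is lost, because 400 mg lies near the centre of the ln(dose) range.

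**Truncation of AUC0-t.** If concentrations fall below quantification sooner at low doses, AUC0-t captures less of the exposure there and the slope rises. For illustration only, captured fractions of 0.80/0.88/0.93/0.96/0.97 from the lowest to the highest dose shift b by +0.076. That is close to the half-width at CV 30% (0.086).

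**The case against.** The strongest reply is that the plan already fits its purpose. The trial is exploratory, its size rests on no hypothesis test, proportionality is not an objective, and descriptive statistics with individual and mean plots suit a search for obvious trends. All of that stands, and it is why the point is minor. The slope could also be fitted later from the same data. Specifying it now only fixes the model and the profiles before results are seen.

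A second reply is that the gain is modest. The interval is informative mainly for large departures, which are also the ones that a plot is most likely to reveal. This stands too. The gain lies in the opposite case, a flat-looking plot, where the interval says how large a departure remains possible. A single slope can miss curvature, so the plot must stay.

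Third, this is not the food-effect method reused. That analysis compares two conditions within subjects in a crossover, whereas this is a regression between subjects in separate cohorts. Only the log scale and the 90% level carry over.

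Two stronger readings are tempting:

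- A reader might infer that the trial plans no estimate of dose proportionality at all. The text available is a synopsis with two procedure schedules, so the absence is shown only for these.
- A reader might infer that fed and fasted 400 mg data would be pooled in the dose plot. The text does not say so. Even at an assumed fed/fasted ratio of 3, pooling would move the slope by only 0.013 (one averaged log value per subject) to 0.019 (all 32 profiles).

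**Conclusion.** The point holds as a minor, inexpensive improvement. As planned, the absence of a visible trend cannot be told apart from imprecision. A slope with a 90% CI would make that distinction, to within about ±0.09 to ±0.21 over assumed CVs of 30 to 80%.

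These figures rest on the assumed CVs, a constant log-scale SD and full evaluability. AUC0-inf may not be estimable in every subject, and notes to both schedules allow sampling to be adjusted after the 100 mg data, so actual precision may be lower. A reader might take the point to mean that the plan is deficient, or that the slope would establish proportionality. Neither follows: the planned method is consistent with the stated objective, and at a true slope of 0.90 the interval would exclude 1 with probability 0.61 at best over these CVs.

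**What to change.** Keep the descriptive statistics and the plots. In the PK analysis section, add an exploratory power model on fasted profiles, reporting b with its 90% CI for Cmax and AUC0-inf. Report AUC0-t as well, with the caveat that earlier loss of quantifiable concentrations at low doses can push its slope upward. Set no pass/fail criterion.

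Repeat the model with only Group A's cycle 1 at 400 mg. Those are first doses taken fasted, as in the other groups, whereas Group B's fasted dose follows a fed dose and the wash-out. In the same edit, state that cross-dose plots use fasted administrations and that 400 mg fasted and fed results are summarised separately.

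The cost is a few lines of text and one regression per parameter, run twice. No new subjects or samples are needed. The downside is an interval that may be wide.

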
The bioequivalence evaluation principle will be used to evaluate whether food affects the bioavailability of TNP-2092 Capsules. That is, if compared with the PK parameters of TNP-2092 Capsules in the fasting state, the 90% confidence intervals of C_{max}, AUC_{0-t} and $AUC_{0-\infty}$ of TNP-2092 Capsule in the fed state are within 80.00% - 125.00% of the corresponding PK parameters, it can be considered that there is no significant difference in the main pharmacokinetic parameters between the two modes of administration, i.e., food has no effect on the pharmacokinetics of TNP-2092 Capsules. The main pharmacokinetic parameters (AUC and C_{max}) are subjected to variance analysis after log transformation, and the geometric mean ratios of AUC_{0-last}, AUC_{0-inf}, C_{max} and their 90% confidence intervals are calculated under the postprandial and fasting administration modes.
		
Safety and tolerability Analysis		

It will be based on the SS. Physical examination results and changes, laboratory test results and changes, vital signs results and changes, as well as ECG results and changes will be subjected to descriptive analysis by dose group and planned time point. The abnormal results of these examinations will also be listed. Adverse events will be coded using the Medical Dictionary for Regulatory Activities (MedDRA), and summarized by treatment group and dose according to the system organ class and preferred terms. In addition, serious adverse events and adverse events leading to dropout and death will be listed separately.
		
Efficacy analysis		
Not applicable.		

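### When the food-effect rule is met, the plan concludes no effect on the pharmacokinetics from Cmax and AUC alone, so a delay that leaves both nearly unchanged would be reported as no effect

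*Combined protocol and SAP*

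**What the plan says.** All references are to the combined protocol and SAP.

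- **Synopsis, Objectives.** The third objective is the effect of eating on the drug's pharmacokinetics, with no restriction to particular parameters.
- **Synopsis, Food effect analysis.** The stated aim is to "evaluate whether food affects the bioavailability of TNP-2092 Capsules". The rule requires the 90% intervals of Cmax, AUC0-t and AUC0-inf to lie within 80.00-125.00%. If they do, "it can be considered that there is no significant difference in the main pharmacokinetic parameters between the two modes of administration", and the same sentence then restates this as "food has no effect on the pharmacokinetics of TNP-2092 Capsules".
- **Same section, model.** "The main pharmacokinetic parameters (AUC and C_{max}) are subjected to variance analysis after log transformation". Geometric mean ratios are promised for two AUCs and Cmax only.
- **Synopsis, Criteria for evaluation.** Tmax is the first PK parameter listed.
- **Synopsis, PK analysis.** "Pharmacokinetic concentration and parameters will be subjected to descriptive analysis by dose group". "The mean and individual drug-time curves will be shown graphically".
- **Synopsis, Plasma sample and Number of subjects.** The 400 mg group has the same sampling times after both doses ("Day 5: Before administration (within 15 minutes), and 0.5 h, 1 h, 2 h, 3 h, 4 h", continuing to 72 h, as on Day 1). The active crossover sample is "16 subjects with 400 mg".

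**The concern.** The rule tests peak and extent of exposure. The sentence it licenses covers the pharmacokinetics as a whole, which includes timing. That sentence is the planned answer to the third objective.

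Tmax appears in neither the rule, the variance analysis nor the promised ratios. Its only stated handling is the general descriptive summary by dose group, which does not name the fed and fasted states, and the plotted curves. Nothing links either of these to the conclusion. Followed as written, the plan could show a later peak after food in its figures and still state that food has no effect.

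The problem arises only when the rule is met. Otherwise the sentence is not made.

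**Working it through.** **No plan figure to reproduce.** The sample size was not based on a hypothesis test. The documents give no within-subject CV, half-life or absorption rate, so the PK values below are assumptions, shown as ranges.

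**Inputs from the documents.** 16 active subjects in a two-period crossover; limits 0.80-1.25; sampling at 0, 0.5, 1, 2, 3, 4, 6, 8, 10, 12, 16, 24, 36, 48 and 72 h in each cycle.

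**Assumed inputs.** One-compartment oral model; absorption rate ka 1.0/h with half-life 8 h, 0.6/h with 8 h, or 1.0/h with 12 h; ka varying between occasions with CV 30% or 50%; between-subject CV 30%; 5% residual error; 8 subjects per sequence; 10,000 trials per setting for the lag results.

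**Step 1: a pure lag.** If food only delays absorption by L hours, the fed curve is the fasted curve moved right by L. True Cmax and AUC0-inf do not change, and Tmax rises by L. With ka = 1.0/h and half-life 8 h, ke = ln 2/8 = 0.0866/h and Tmax = ln(ka/ke)/(ka - ke) = 2.68 h. A 2 h lag makes it 4.68 h. On the planned sampling times, without noise, 24 cases were computed (lag 1-4 h; half-life 4, 8 or 12 h; ka 0.5 or 1.0/h). Observed Tmax moved later by 1 to 5 h. The fed/fasted ratios stayed at 0.953-1.013 for Cmax, 0.948-0.997 for AUC0-72 and 0.948-0.998 for AUC0-inf.

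**Step 2: slower absorption.** If food lowers ka, the peak falls, because Cmax is proportional to exp(-ke × Tmax). For half-life 8 h:

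- ka 1.0 to 0.5/h: Tmax 2.68 to 4.24 h; Cmax ratio 0.6925/0.7929 = 0.87.
- ka 1.0 to 0.4/h: Tmax 2.68 to 4.88 h; Cmax ratio 0.6551/0.7929 = 0.83.

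These two cases, ka 0.6 to 0.3/h (half-life 8 h) and ka 1.0 to 0.4/h (half-life 12 h) were simulated with ka CV 30%. Mean observed Tmax moved by about 1.4-2.7 h and the Cmax ratio was about 0.82-0.87.

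**Step 3: how often the rule is met.** The half-width of the 90% interval on the log scale is about t(0.95; 14) × s × √(2/16), with t = 1.761 and s = √ln(1 + CV²). The third column assumes a point ratio of 1. The last three columns are simulated percentages of trials in which the rule is met.

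| Within-subject CV | Half-width | Interval at ratio 1 | No delay | Pure 2 h lag | Slower absorption |
|---|---|---|---|---|---|
| 15% | 0.093 | 0.911-1.097 | 88-96 | 87-95 | about 11-38 |
| 20% | 0.123 | 0.884-1.131 | 65-79 | 64-76 | about 5-22 |
| 25% | 0.153 | 0.858-1.166 | 38-50 | 39-48 | about 1-8 |
| 30% | 0.183 | 0.833-1.201 | 19-27 | 19-25 | under 3 |
| 40% | 0.240 | 0.787-1.271 | 3-5 | 3-4 | not computed |

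The largest drop in pass rate caused by a pure 2 h lag in any setting is 4.5 percentage points. Simulation error matters little: a repeat with 4,000 trials per setting reached 9% in the slower-absorption column at CV 25%.

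**Step 4: what a Tmax estimate would show.** The interval is formed from the Walsh averages of 16 paired differences (36th smallest to 36th largest). Its exact coverage is 90.7% for continuous data. Over all pure-lag trials it excluded 0 in 89-99.8% with a 2 h lag, 35-63% with a 1 h lag and 1.0-2.8% with none. The last figure means actual coverage of 100 - 2.8 = 97.2% to 100 - 1.0 = 99.0%. Tmax can take only the scheduled times, so many differences tie and the interval is conservative.

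**The case against.** Four arguments deserve weight.

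1. **The wording has a local scope.** The section opens with bioavailability and defines the main parameters as AUC and Cmax, so the last clause can be read as a loose restatement. A reader of the whole paragraph may take it that way. But a report would carry the conclusion, and the conclusion answers an objective that is not limited to AUC and Cmax.
2. **A delay would not be hidden.** A reader might infer that the plan ignores Tmax. The documents do not support that: Tmax is estimated and summarised, and individual and mean curves are plotted, so a delay could be noticed. What stands is that none of this bears on the stated conclusion.
3. **The text is a synopsis with two schedules.** It does not show that no Tmax comparison is planned anywhere, only that none is stated here. The over-wide conclusion, however, is present text and not an inference from missing pages.
4. **The mechanism drives the size.** A pure lag leaves Cmax and AUC unchanged by construction, so the rule's blindness to it is built into the model. If food slows absorption, Cmax falls and the rule usually fails. This stands in full. A reader might infer that the rule misses any food-induced delay, and that would be too strong.

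**Conclusion.** The point holds in a limited form. When the rule is met, the conclusion claims more than was tested, and it would be wrong for a delay that leaves Cmax and AUC nearly unchanged.

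How likely that is cannot be settled from the documents, because they give neither the variability nor the mechanism. For a pure 2 h lag, the over-wide statement would be made in most trials at CV 15-20%, in somewhat under half at 25%, and in a quarter or fewer at 30%. For slowed absorption it would be made in a minority of trials even at CV 15%, and rarely at 25% or above. A reader might infer that this trial will probably give a false no-effect statement. That inference needs both low variability and a nearly pure lag, and the documents establish neither.

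The logical gap itself does not depend on the simulations. Severity is minor to moderate: no subject, sample or existing estimate is affected, but a prespecified answer to a stated objective can be wrong as written.

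**What to change.** 1. **Narrow the conclusion.** On a pass, state only that there is *no relevant effect of food on Cmax and AUC (peak and extent of exposure)*. This alone closes the logical gap.
2. **Add timing, so that the third objective covers it.** Summarise Tmax separately for the fed and fasted states. Report the paired fed-minus-fasted median difference with a non-parametric 90% interval (for example Hodges-Lehmann) in active 400 mg subjects evaluable in both cycles. Present it as a descriptive estimate beside the rule, not as a further test.
3. **State the interval's limits.** Say that it is conservative because Tmax is tied on the sampling times (actual coverage about 97-99% in the cases above). An interval that includes 0 does not show that there is no delay.

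**Cost.** SAP wording and one summary of data already planned; no new samples or subjects. The permitted conclusion becomes narrower, and sensitivity to a delay of about 1 h is limited (35-63%). A version that allows for period costs little: at CV 20% it excluded 0 in 35-62% of trials for 1 h and 89-99.8% for 2 h with 8 subjects per sequence, and in 30-55% and 81-99% if dropouts left 8 and 5. Sensitivity also depends on the sampling times, which Appendix 2, note 5 allows to be adjusted after the 100 mg results, so any change near the peak should be considered when this estimate is read.
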